6.9 Follow-up/End of Study Visit (Day 112)

Subjects will return to the study site having fasted for \geq 8 hours, and the following assessments will be performed:

- AEs
- concomitant medications
- weight
- vital signs
- 12-lead ECG (if previously abnormal)
- complete physical examination
- clinical laboratory evaluations (including haematology, coagulation, serum chemistry [fasting], CRP, and UA; see [Appendix B](#))
- PML subjective checklist (see [Appendix D](#)); any positive responses to the PML subjective checklist will require that the PML objective checklist be performed by the Investigator according to [Appendix D](#) and the study manual
- serum pregnancy test (WOCBP)
- partial Mayo Score assessment (rectal bleeding, stool frequency, PGA subscores only)
- faecal calprotectin
- ADA testing

Subjects will also be asked to confirm and provide all relevant contact information for the 6-month phone visit.

6.10 6 Months Post-Treatment (Final Phone Follow-up)

Study subjects will receive a follow-up phone call at the 6-month post-treatment time point (Day 252) or earlier if the subject terminates early from the study. During this call, the PML subjective checklist ([Appendix D](#)) will be administered and the data recorded in the CRF. Any positive responses to the PML subjective checklist will necessitate the scheduling of an additional site visit so that the PML objective checklist may be performed by the Investigator according to [Appendix D](#) and the study manual.

6.11 Efficacy Assessments

6.11.1 Mayo Score

Clinical remission, clinical response, endoscopic response, endoscopic remission, complete and partial Mayo Score and individual endoscopy, rectal bleeding, and stool frequency subscores will be assessed using the Mayo Score (see [Appendix A](#)).

Subjects will record stool frequency and rectal bleeding subscores in an electronic subject diary each day through the entire treatment and follow-up periods. Subjects will be provided standardised instructions for recording the number of stools and their worst rectal bleeding over a 24-hour period ([Appendix A](#)). Each subscore ranges from 0 to 3, with higher scores indicating more severe disease. For visits that include a sigmoidoscopy, data collected on the day of the bowel preparation will not be used to assess the Mayo Score. The nearest 3 available days preceding the study visit (or bowel preparation) will be used to assess the Mayo Score, allowing for discontinuous days if a day is missing (eg, Day -4, Day -3, Day -1 [with Day -2 missing]). However, if the subject has a combined Screening visit, then the baseline Mayo Score for stool frequency and rectal bleeding should be done before the day of randomization for final determination of eligibility.

Endoscopic subscore will be assessed by a central reading of recorded endoscopy scans. Sigmoidoscopy will be performed by the site endoscopist and scored by a blinded central reader reviewing video recordings of the procedure. Further details to standardise procedures, video recordings/equipment, and assessment of endoscopy will be provided in the laboratory manual.

The complete Mayo Score is a sum of 4 subscores (ie, stool frequency, rectal bleeding, endoscopic findings, and PGA). The complete Mayo Score ranges from 0 to 12 using all 4 subscores.

Partial Mayo Score (range 0 to 9) will include the PGA, stool frequency, and rectal bleeding subscores only.

At baseline and Day 84 (or Early Termination), complete Mayo Score will be assessed and recorded.

For evaluation of the primary endpoint clinical remission, the PGA subscore will **not** be evaluated, only the stool frequency, rectal bleeding, and endoscopic subscores will be assessed ([Section 7.4](#)). Clinical response will be assessed using the stool frequency and rectal bleeding subscores.

6.11.2 Colonic Biopsy

Colonic biopsies will be obtained from subjects during sigmoidoscopy at baseline (within 14 days prior to randomisation) and at Week 12 (Day 84). Biopsies will be taken from the most inflamed area of the colon, while avoiding necrotic areas of ulcerated mucosa or suture sites in patients with previous colonic resection. Biopsies should be repeated from the same area at baseline and at Week 12. Biopsies will be placed into RNA*later*® (Life Technologies Corporation, Carlsbad, CA, United States of America [USA]) or formalin for storage and subsequent processing. Further details regarding the biopsy collection, processing, storage, and shipment will be provided in the laboratory manual. Colonic biopsies will be subjected to histologic evaluation and immunohistochemistry. Histologic assessment will be performed.

All biopsies will be read by a central laboratory. Further details will be provided in the laboratory manual.

6.11.3 Faecal Calprotectin

Stool samples will be collected by the study subjects and brought to the study centre for faecal calprotectin assessment at the designated time points. The stool should be a morning specimen. Subjects will be provided instructions regarding the proper means of collecting (including proper collection time), processing (eg, mixing), and storing the stool samples.

Further details will be provided in the laboratory manual.

6.11.4 IBDQ

Health-related quality of life will be assessed by the IBDQ (see [Appendix G](#)),¹⁶ a standardised validated questionnaire with scores ranging from 32 to 224 points, at time points designated in the study schedule ([Table 6-1](#)).

6.12 Pharmacokinetic and Pharmacodynamic Assessments

6.12.1 Pharmacokinetic Blood Sample Collection, Processing, and Analysis

Blood (4 mL) samples for PK analysis will be obtained in K₂EDTA tubes according to the site standard operating procedures (SOPs) prior to dosing and at the time points delineated in the study schedule ([Table 6-1](#)). All samples (except those collected postdose on Days 0 and 84) should be obtained prior to the daily dosing of study drug (ie, C_{trough}). The actual collection time of each sample must be recorded in the source data, collection tube, and on the electronic CRF (eCRF). The allowed time deviation window for blood sample collection is ± 20 minutes for the samples up to 4 hours postdose on Days 0 and 84.

The Sponsor will supply complete written instructions for collection, handling, processing, storage, and shipping of samples in the laboratory manual.

Plasma PK sample analysis will be performed using validated procedures and methods.

6.12.2 Pharmacodynamic Blood Sample Collection, Processing, and Analysis

Pharmacodynamic assessments will be measured from 2 mL blood samples collected in heparinised blood collection tubes from subjects at selected sites according to the study schedule ([Table 6-1](#)). The blood samples will be analysed by FACS for PTG-100 RO and $\alpha\beta7$ RE in peripheral blood lymphocytes. The percentages of circulating lymphocytes will also be measured.

An additional 3 mL blood sample will be collected in heparinised blood collection tubes at selected sites (Day 0 predose only) with plasma stored for exploratory immunologic assessments.

The Sponsor will supply complete written instructions for the collection, handling, processing, storage, and shipping of samples in the laboratory manual. The samples will be analysed using validated assay methods.

6.12.3 Anti-drug Antibody Blood Sample Collection and Processing

Blood samples (3 mL) will be collected in heparinised blood collection tubes according to the study schedule ([Table 6-1](#)) and serum will be evaluated for the presence of ADAs with a bridging immunoassay.

The Sponsor will supply complete written instructions for the collection, handling, processing, storage, and shipping of samples in the laboratory manual.

6.13 Safety Monitoring

Subjects will be monitored for AEs and concomitant medication use throughout the study. Physical examination (including weight and vital signs), clinical safety labs, PML assessments, and ECGs will be done periodically throughout the study according to the schedule specified in [Table 6-1](#). Safety evaluations may be repeated at the Investigator's (or designee's) discretion.

The following will constitute AEs of special interest that will be monitored at each visit: serious or opportunistic infection (viral, bacterial, fungal including systemic/gut localization), allergic/drug reactions, immune system disorders, and/or suspected PML. Adverse events of special interest will not constitute Investigational New Drug safety reports unless they are defined as serious events and there is evidence suggesting a causal relationship between the drug and the event.

The JCV antibody testing must have been performed and documented on all randomised subjects within 90 days prior to dosing. All subjects will be closely monitored for signs and symptoms of PML through directed questionnaires that assess recent changes in vision, speech, gait, sensation, comprehension, coordination, and personality, with any positive responses prompting objective testing^{1,17} by the Investigator (see [Appendix D](#)).

An independent DMC will be appointed to monitor the safety of the subjects in the study. The DMC will meet approximately quarterly to review the safety data and will make recommendations regarding the continuation, modification, suspension, or termination of the study. Operational guidelines will be specified in the DMC charter.

Every effort will be made to schedule and perform the procedures in accordance with the nominal time, giving considerations to appropriate posture conditions, practical restrictions, and the other procedures to be performed at the same time point. Acceptable

windows for study visits are provided in [Section 6.1](#). The order of priority for scheduling procedures around a time point is (in descending order of priority):

- dosing
- PK blood sampling
- PD blood sampling
- vital sign measurements
- ECGs
- blood and urine samples for clinical laboratories
- physical examinations

6.13.1 PML Monitoring

Any subject with abnormal neurological examination at Screening will be excluded from participation in the study.

The JCV antibody testing must have been performed and documented on all randomised subjects within 90 days prior to dosing.

All randomised subjects will be closely monitored for signs and symptoms of PML through directed questionnaires that assess recent changes in vision, speech, gait, sensation, comprehension, coordination, and personality, with any positive responses prompting objective testing by the Investigator (see [Appendix D](#)).^{1,17,26,27} All randomised study subjects will be closely monitored for the onset of any new neurological signs or symptoms or suspected PML during treatment and follow-up. The study's monitoring program will include education of site personnel and subjects about the signs and symptoms of PML and will advise subjects to report to designated personnel should they experience any signs and symptoms suggestive of PML.

Study sites will be provided a stepwise algorithm for the action plan for all subjects with suspected PML during the study and follow-up period; details regarding this algorithm will be provided in the study manual. Appropriately qualified site staff will complete the subjective PML checklist using the questionnaire ([Appendix D](#)) at all study visits per the schedule in [Section 6.1](#). If any subject has a positive response based on the PML subjective checklist, the site will immediately schedule a visit where the Investigator will perform the PML objective checklist (involving tests of visual fields, ocular motility, speech, muscle strength, gait, memory, and sensation) per [Appendix D](#) and the study manual. If a study subject has both positive subjective and objective checklists, the subject will be referred to a local neurologist for further evaluation to rule out PML. If

the neurologist cannot rule out PML, the case will be referred to the Independent Adjudication Committee (that will include at least one neurologist) for the final determination of PML.

6.13.2 Adverse Events

Adverse event definitions; assignment of severity, causality, action taken, and outcome; and procedures for reporting SAEs are detailed in [Appendix F](#).

Subjects will be asked a nonleading question such as “Have there been any changes in your health status since Screening/since you were last asked?” at the time points specified in [Table 6-1](#) to assess for the occurrence of AEs. Subjects will also be encouraged to voluntarily report AEs occurring at any other time during the study.

All nonserious AEs, whether volunteered, elicited, or noted on physical examination, will be recorded from Day 0 until study completion. Serious AEs will be recorded from the time the subject signs the ICF until study completion.

All AEs (nonserious and serious) should be followed until the event has resolved, returned to baseline, or is assessed as stable by the Investigator (or designee).

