The schematic of the study design is displayed in Figure 4-2. The start of the study is defined as the date the first subject enrolled in the study (ie, signs an Informed Consent Form [ICF]). A subject who completes the Day 112 Follow-up visit is considered to have completed the study. Completion of the study does not include any unplanned Follow-up visits (eg, return to the clinic for repeat clinical laboratory) or the phone visit approximately 6 months after the end of treatment. The end of the study is defined as the date the last subject completes the study (or completes an Early Termination visit). The planned duration of study conduct is approximately 17 to 20 months from Screening through the final subject's Follow-up visit (up to 42 days of screening + 12- to 15-month enrolment + 12 weeks treatment + 28 days follow-up).

Figure 4-2 Study Design Schematic

Phase 2b in UC patients: 12 Week Induction
Randomised, Double-blind, Placebo-controlled Adaptive Design

ADA = anti-drug antibodies; IBDQ = Inflammatory Bowel Disease Questionnaire; PD = pharmacodynamics; PK = pharmacokinetics; QD = once daily; TNF α = tumour necrosis factor-alpha; UC = ulcerative colitis.

In this study, the primary efficacy endpoint is clinical remission as defined by the rectal bleeding, stool frequency, and endoscopic subscores of the Mayo Score; clinical response, endoscopic response, and endoscopic remission will be determined using designated subscores of the Mayo Score assessment (see [Section 7.4](#) for details). Changes in complete and partial Mayo Score, rectal bleeding subscore, stool frequency subscore, and endoscopic subscore will be evaluated at designated time points. The IBDQ questionnaire will be assessed pre- and post-treatment; sigmoidoscopy and biopsy will be performed at baseline and Day 84 for evaluation of endoscopic response and remission and histological assessment. Stool samples will be collected for faecal calprotectin at designated time points. Subject blood samples will be obtained at designated time points from Day 0 through Day 112 for analysis of safety labs, PK, PD, and ADA parameters.

Safety will be monitored with AE inquiries, assessment of concomitant medication use, clinical laboratory evaluations ([Appendix B](#)), vital sign measurements, 12-lead ECGs, and physical examination findings during the study. A PML assessment will also be done at designated time points. A study flow chart is presented in [Table 6-1](#).

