6 STUDY PROCEDURES

6.1 Schedule of Study Procedures

A study flow chart is presented in [Table 6-1](#). The total blood volume that will be taken during the study is outlined in [Appendix E](#).

Table 6-1 Study Flow Chart

	Screening	Randomisation Period	Treatment								Follow up		Early Termination ³
	Days -42 to -7	Day -7 to Day -1	Day 0 (pre-dose) ¹	Day 0 (dosing, post-dose)	Day 14 ±3 days	Day 28 ±3 days	Day 42 ±3 days	Day 56 ±3 days	Day 70 ² ±3 days	Day 84 ±3 days	Day 112 ±7 days	Day 252 ² ±30 days	
Informed Consent	X												
Demographics	X												
Medical History	X												
Prior and Concomitant Medications ⁴	X		X	X	X	X	X	X	X	X	X		X
Inclusion/Exclusion	X												
Height	X												
Weight	X		X		X	X	X	X		X	X		X
Physical Examination ⁵	X		X	X	X	X	X	X		X	X		X
Vital Signs ⁶	X		X	X ⁷	X	X	X	X		X	X		X
12-lead ECG ⁶	X		X ⁸		X			X		X	X ⁹		X
Laboratory: Haematology, Coagulation, Serum Chemistry ¹⁰	X		X		X	X		X		X	X		X
Stool C.diff , Culture, and Ova and Parasites	X												
Urinalysis (microscopy if abnormal)	X		X		X	X		X		X	X		X
PML Neurological Assessment ¹¹	X		X		X	X	X	X	X	X	X	X	X
Hepatitis B & C; TB Test	X												
Serum Pregnancy (WOCBP)	X									X	X		X

	Screening	Randomisation Period	Treatment								Follow up		Early Termination ³
	Days -42 to -7	Day -7 to Day -1	Day 0 (pre-dose) ¹	Day 0 (dosing, post-dose)	Day 14 ±3 days	Day 28 ±3 days	Day 42 ±3 days	Day 56 ±3 days	Day 70 ² ±3 days	Day 84 ±3 days	Day 112 ±7 days	Day 252 ² ±30 days	
Sigmoidoscopy	X ¹²									X			X
Colonic Biopsy	X ¹²									X			X
Mayo Score ¹³	X ¹²				X	X	X	X	X	X	X		X
JCV Antibody Testing ¹⁴	X ¹⁴												
Confirmation of Eligibility			X										
Randomisation ¹⁵		X											
Adverse Events			X	X	X	X	X	X	X	X	X		X
IBDQ			X							X			X
Faecal Calprotectin			X				X			X	X		X
Urine Pregnancy (WOCBP)			X		X	X	X	X					
PK Blood Collection ¹⁶			X	X ¹⁷	X	X	X	X		X ¹⁷			X ¹⁷
PD Blood Collection ¹⁶			X	X ¹⁷	X	X	X	X		X ¹⁷			X ¹⁷
ADA Testing			X			X		X		X	X		X
Exploratory Immunologic Assessment Blood Sample ¹⁸			X										
IP Administration ¹⁹				X	X	X	X	X	X	X			

ADA = anti-drug antibodies; AE = adverse event; ECG = electrocardiogram; IBDQ = Inflammatory Bowel Disease Questionnaire; IP = investigational product; JCV= John Cunningham virus; PD = pharmacodynamics; PK = pharmacokinetics; PML = progressive multifocal leukoencephalopathy; TB = tuberculosis; WOCBP = women of childbearing potential.

¹ All predose procedures should be completed prior to dosing.

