APPENDIX D - PROGRESSIVE MULTIFOCAL LEUKOENCEPHALOPATHY (PML) ASSESSMENT^{26,27}

A subjective PML checklist (see table below) is to be administered by appropriately qualified site personnel (Investigator or Study Coordinator) to all subjects at Screening, at the designated time points as noted in [Table 6-1](#), and whenever new neurologic symptoms manifest. For each symptom in the subjective checklist that had positive findings, results of an objective evaluation (see below), administered by the Investigator to assess corresponding neurologic function, are to be recorded on the objective checklist and an AE recorded.

Subjective PML Checklist

Symptoms	"Compared to how you usually feel, have you had a significant change in any of the following?"		If the answer is "Yes", obtain a description of the symptom(s) with examples.	Applicable Objective Test(s): Document results on PML Objective Checklist
	Yes	No		
1. Have you been experiencing any persistent difficulty with your vision such as loss of vision or double vision? Have you been having trouble with reading?				Test visual fields and ocular motility.
2. Have you been experiencing any persistent difficulty speaking or having your speech understood by others?				Casual observation of speech output for dysarthria or aphasia. Ask patients to name a few objects and repeat a multipart phrase.
3. Have you been experiencing any persistent weakness in an arm or a leg?				Test for pronator drift (Barré maneuver) and/or fixation on arm roll. Assess the ability to hop on either foot; foot and finger tapping. Test symmetric muscle strength.
4. Have you noticed yourself regularly bumping into things or having difficulty writing?				Ask for spontaneous writing sample and observe finger to nose, heel to shin, and tandem gait.
5. Have you regularly been experiencing difficulty understanding others?				Ability to follow serial commands (Close your eyes, stick out your tongue, and touch your left finger to your left ear)
6. Have you had persistent problems with your memory or thinking?				Recall of 3 objects over 1 minute with distraction; ability to follow commands.
7. Have you been experiencing any persistent numbness or other loss of sensation?				Test sensation side to side with pinprick.

Objective PML Checklist

Positive Symptom(s)	Applicable Objective Test(s)	Test Result(s)		If test result is abnormal, briefly describe result
		Normal	Abnormal	

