### 4.8.1. Adverse Events

The primary safety endpoint is the proportion of subjects with at least 1 AE comparing individual PTG-100 dose groups with placebo.

Secondary endpoints (all based on comparison of individual PTG-100 dose levels to placebo) will include:

- Frequency and type of AEs (affecting  $\geq 5\%$  of subjects)
- Proportion of subjects with at least 1 SAE
- Number and type of SAEs
- Frequency of adverse events of special interest (AESI) including serious or opportunistic infection (viral, bacterial, fungal including systemic/ gut localization), allergic/ drug reactions, immune system disorders, and PML or new onset neurologic symptoms

Adverse events will be coded using the Medical Dictionary for Regulatory Activities (MedDRA) and displayed in tables and listings using System Organ Class (SOC) and Preferred Term.

Analyses of adverse events will be performed for those events that are considered treatment emergent, where treatment emergent is defined as any adverse event with onset after the administration of study medication through the end of the study visit or any event that was present at baseline but worsened in intensity or was subsequently considered drug-related by the investigator through the end of the study.

Adverse events are summarized by subject incidence rates, therefore, in any tabulation, a subject contributes only once to the count for a given adverse event (SOC or preferred term).

The number and percentage of subjects

- with any treatment-emergent adverse event
- with any treatment-emergent adverse events assessed by the Investigator as related to treatment (definite, probable, or possible relationship)
- with any treatment-emergent serious adverse event
- with treatment-emergent adverse events by severity
- with adverse events affecting  $\geq 5\%$  of subjects within any treatment group across both stages of the study
- with AESI

will be summarized by treatment group and overall. In addition, all active groups will be pooled in the summaries for comparison to placebo. In these tabulations, each subject will contribute

only once (i.e., the most related occurrence or the most intense occurrence) to each of the incidence rates in the descriptive analysis, regardless of the number of episodes.

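### The protocol contradicts itself on whether a PML case found at the Day 252 call is recorded as an adverse event, and the SAP leaves new-onset events after Day 112 out of its by-arm safety summaries

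*Protocol*

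**What the plan says.** **Passages that close recording at Day 112.** Protocol Section 6.13.2 gives both windows. Non-serious events "will be recorded from Day 0 until study completion"; for serious events, "Serious AEs will be recorded from the time the subject signs the ICF until study completion". Section 4.1 then defines completion for a subject: "A subject who completes the Day 112 Follow-up visit is considered to have completed the study". It adds that completion does not extend to unplanned visits "or the phone visit approximately 6 months after the end of treatment". Table 6-1 gives the call its own column ("Day 252 ² ±30 days"). Only the PML assessment row is marked there; the Adverse Events and the Prior and Concomitant Medications rows are blank.

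**Passages that keep it open.** Appendix D applies the subjective checklist at the Table 6-1 time points and whenever new neurological symptoms appear. For each positive symptom, the objective results "are to be recorded on the objective checklist and an AE recorded". Appendix F asks for every serious event after consent and gives no closing date. Its definition of a treatment-emergent event also has no end.

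**What happens at the call.** Under Section 6.10 the checklist goes into the CRF. "Any positive responses to the PML subjective checklist will necessitate the scheduling of an additional site visit". Section 6.13.1 continues to a local neurologist and, if PML cannot be ruled out, to an adjudication committee.

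**SAP.** The schedule in Section 2.4 has no Day 252 column, and its footnote on telephone contacts covers only Day 70. Section 4.8.1 names PML or newly arising neurological symptoms as events of special interest. It restricts adverse event analyses to treatment-emergent events, which for new events means those "with onset after the administration of study medication through the end of the study visit". It separately promises a listing of all on-study events, including follow-up. Sections 7.1 and 7.2 contain no output for PML checklists, referrals, adjudication results or John Cunningham virus (JCV) antibody status. Section 5 reports no change from the protocol's analyses.

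**The concern.** The Day 252 call has one scheduled procedure, the PML assessment, and its purpose is to find late cases of a named event of special interest. The protocol builds the route from a positive answer to adjudication, but it gives sites two incompatible instructions on whether the finding enters the adverse event database. A site working from Sections 4.1 and 6.13.2 and Table 6-1 could leave it out. A site working from the appendices would record it. Ascertainment of a rare and serious event could then differ between sites.

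The SAP adds a second problem that remains even if every site records the event. An event with onset after Day 112 falls outside the SAP's treatment-emergent window, so the by-arm special-interest summary could show no PML while the CRF for the call, or a listing, holds a case. This is the first trial of PTG-100 in ulcerative colitis (Protocol Section 2.2), so what the report can say about PML matters. Concomitant medication is also not scheduled at the call, so later exposure to other immunosuppressants or biologics would not be collected systematically.

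**Working it through.** **1. Timing of the call.** Treatment ends at Day 84. Counting six 28-day months, 84 + 6 × 28 = 252, which matches Table 6-1. Six calendar months gives 84 + 6 × 30.4375 ≈ 267, inside the ±30-day window (Days 222 to 282).

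**2. Gap between the close of recording and the call.**
- Nominal: 252 − 112 = 140 days.
- Shortest, using both visit windows: (252 − 30) − (112 + 7) = 222 − 119 = 103 days.
- Longest: (252 + 30) − (112 − 7) = 282 − 105 = 177 days.
- Share of the post-treatment interval: 140 / (252 − 84) = 140/168 = 83%.
- Early terminators: Section 6.8 encourages safety assessments through 28 days, and the call is due 6 months after discontinuation. The gap is 168 − 28 = 140 days, or 183 − 28 = 155 days by calendar months. Section 4.1 gives no completion date for a subject who never attends Day 112.

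**3. One positive checklist answer at Day 252, passage by passage.**

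| Source | Adverse event record required? |
|---|---|
| Protocol 6.13.2 with 4.1 | No; window closed at Day 112 |
| Protocol Table 6-1, Day 252 column | Not scheduled |
| Protocol 6.10 | Checklist in CRF and a site visit; silent on an event record |
| Protocol Appendix D | Yes, for each positive symptom |
| Protocol Appendix F | Yes, if serious; no end date |

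**4. The same case in the SAP outputs.**
- Not recorded as an event: it stays in the CRF for the call, and no planned output reads that form.
- Recorded, onset after Day 112: not treatment-emergent under the new-onset part of SAP Section 4.8.1, so absent from the incidence summaries and the special-interest count. It could appear in Table 14.3.2.1 (deaths), Table 14.3.2.2 (serious events) or Listing 16.2.7.1.
- Recorded, onset on or before Day 112 but first reported at the call: it meets the SAP window and would be counted.

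Under the protocol's own treatment-emergent definition, the second of these cases would count. The SAP is narrower and does not say so.

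**5. Alternative reading of completion.** If completion meant the end of the whole trial (the last subject's Day 112 or Early Termination visit), a subject's nominal call falls inside the window only if first dosing was at least 252 − 112 = 140 days before that of the last subject. With even enrolment over the planned 12 to 15 months (about 365 to 457 days; the evenness is an assumption), 140/457 = 31% to 140/365 = 38% of subjects would still fall outside.

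**The case against.** The best defence is that the protocol does provide for late PML. Appendix D requires the event record, Appendix F has no closing date for serious events, and its 24-hour notification rule for potentially reportable events has none either. Section 6.13 monitors events of special interest at every visit, and Section 4.1 calls the 6-month contact a phone visit. Detection, examination, referral and adjudication are all described. The SAP schedule looks like an older copy: it has screening from Day −35 where the protocol has Day −42, and a 3-minute rest where the protocol has 5. The missing column may therefore be version lag and not a decision to drop the data.

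Much of this stands, and it rules out three stronger readings.
- A reader might infer that the plan lets a late PML case go unrecorded as a serious event. The documents do not support that: two appendices require the record. The fault is a conflict between passages.
- A reader might infer that nothing found at Day 252 can reach any planned output. That also fails, because the serious-event, death and all-event listings are not confined to treatment-emergent events.
- A reader might turn the gap into exposure, 240 × 140 / 365.25 ≈ 92 person-years, and treat that as the loss. It is calendar arithmetic: it assumes 240 completers and no dropout, includes placebo and carries no PML rate. It says nothing about how many events could be missed.

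Nor can it be said that a late event could never be separated from later therapy. The site visit, neurologist and adjudication committee may take a drug history.

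The defence does not remove the conflict between Sections 4.1 and 6.13.2 and the appendices, and version lag does not supply the missing SAP window or listing.

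**Conclusion.** The point holds as a conflict within the protocol and a gap in the SAP. Recording closes at Day 112 in one set of passages and stays open in another, so capture of a late PML case depends on the passage a site follows. Even if captured, a case with onset in the nominal 140 days (103 to 177) between the Day 112 visit and the call would be missing from the by-arm treatment-emergent and special-interest summaries.

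This should be fixed, but it does not touch the primary efficacy endpoint, type 1 error or on-treatment safety. No expected number of missed cases can be given, because the documents contain no PML rate.

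Assumptions: completion is read at subject level, as Section 4.1 defines it. The SAP's end-of-study visit is Day 112, as the title of Protocol Section 6.9 indicates. The SAP's restriction to treatment-emergent events governs its special-interest count, although that bullet does not repeat the term. The DMC charter and study manual were not available and could clarify site practice.

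**What to change.** **Protocol**
- Reconcile Sections 4.1 and 6.13.2 and Table 6-1 with Appendices D and F, so that serious events and suspected-PML or neurological events are recorded through the 6-month call. State the same for early terminators.
- Add an Adverse Events entry at Day 252 in Table 6-1. A concomitant medication entry limited to biologics and immunosuppressants is preferable but secondary.

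**SAP**
- Add the Day 252 column to the schedule.
- Count the PML and neurological events of special interest through Day 252, separately from the treatment-emergent window, and declare the difference from the protocol's treatment-emergent definition in Section 5.
- Add one listing by arm of positive checklists, referrals, adjudication results and JCV status.

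**Cost.** Wording in two documents, one or two fields on a call already scheduled, and one count and one listing. The drawback is a small supplementary safety data transfer after the main lock, since the last subjects' calls come after the defined end of study.
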